9.2. Time period for collection

The study period during which all Aes and SAEs must be reported begins after informed consent is obtained and ends 30 days following the last administration of any study treatment (safety follow up visit). If the safety follow-up visit is performed less than 30 days after the last IMP administration, any AE / SAE occurring between the safety follow-up visit until 30 days after last study treatment administration will be considered as AE / SAE and notified to Transgene, regardless of their relationship to IMP(s).

After this period, and until day 90 after last administration of study treatment (i.e. until safety follow-up phone call) investigators should report treatment-related non-serious AE and all SAEs. Ongoing SAEs at the 90-day safety follow-up phone call must be followed up until stabilization or until the outcome is known, unless the patient is documented as “lost to follow up”.

SAEs occurring more than 90 days after administration of the last dose of any study treatments, and evaluated by the investigator as related to the IMP(s) should be collected and reported to the sponsor indefinitely even after study closure. These will however not be reported in the eCRF after Database lock.

If an Adverse Event occurs during the screening period (i.e., after ICF signature and before start of study treatment), it will be recorded either on a “Medical history/ current conditions” page for an identified syndrome (e.g., pneumonia) or on a “Signs and symptoms” page for symptoms with no associated syndrome (e.g., diarrhoea).

From start of study treatment, AEs will be recorded on an “AE” page. In case of worsening of a medical condition which started before start of study treatment, an AE page will be completed using a verbatim starting by “worsening of...”.

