7.2. Baseline

The following evaluations must be performed within 21 days prior to the initiation of treatment:

- Inclusion/exclusion criteria check

- Physical examination of the major organ system, including vital signs, weight and height
- PS on ECOG scale
- Demography
- History of studied disease (including prior antineoplastic treatments)
- Relevant medical history / current medical conditions and signs and symptoms
- Serious adverse events reporting (from the date of signature of the ICF)
- Concomitant medications and significant non-drug therapies collection and medications administered during the month prior to start of study treatment
- Tumor sample on biopsy (mandatory for phase Ib and phase II part 1; mandatory only for patients with accessible lesions in phase II part 2)
- HPV status
- HIV and HCV serology, detection of antigen HBs for phase II part 2
- Tumor evaluation
 - by preferably CT (or MRI) of the head and neck, chest, abdomen and all other known sites of disease (e.g. pelvis, if applicable) and other established assessments of tumor burden if CT / MRI imaging is insufficient for the individual patient. In case of bone pain, an adequate radiological and/or isotopical exploration is to be performed to research metastases

The following evaluations must be performed within 7 days prior to the initiation of treatment, within 3 days prior to randomization for phase II part 2:

- Inclusion/exclusion criteria check
- 12-leads Electrocardiogram
- Pulse oximetry on room air only for phase II part 2
- Blood analyses:
 - Hematology, biochemistry, creatinine,
 - Free T4, TSH
 - HIV and HCV serology, detection of antigen HBs only for phase Ib and phase II part 1
 - Pregnancy test for women of childbearing potential
 - Blood sample collection for immunomonitoring

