9.1. Definitions

Treatment Emergent Adverse Event (TEAE)

A treatment-emergent adverse event (TEAE) is defined as a sign or symptom that emerges during treatment or within 30 days of the last dose of the study drug, having been absent pre-treatment or that has worsened relative to the pre-treatment state. Any adverse event deemed

related to study drug will also be considered a TEAE regardless of elapsed time since last study drug dose.

Adverse Event (AE)

An AE for the purposes of this protocol is a medical occurrence or deterioration of a pre-existing medical condition occurring after signing the informed consent and even if the event is not considered to be related to the study treatment(s).

Preexisting medical conditions (other than the condition being studied) judged by the investigator to have worsened in severity or frequency or changed in character during the protocol-specified AE reporting period.

Adverse reaction (AR):

All noxious and unintended responses to a medicinal study product (TG4001 or avelumab) related to any dose or to a study specific procedure.

Laboratory abnormality

A laboratory abnormality is reported as an AE if it is out of range, considered by the Investigator as clinically significant (i.e. with clinical manifestations or requiring treatment or clinical management).

Other significant abnormalities

Any significant worsening noted during interim or final physical examinations, electrocardiograms, x-rays, and any other potential safety assessments, whether or not these procedures are required by the protocol, should also be recorded as a non serious or serious AE, as appropriate, and reported accordingly.

Other significant adverse events

Any events and any laboratory abnormalities that led to an intervention, including withdrawal / dose reduction of IMP or significant additional concomitant therapy other than those reported as SAE, and that are considered by Transgene or the Investigator to be of special interest because of clinical importance.

Serious Adverse Event (SAE) / Serious Adverse Reaction (SAR) / Suspected Unexpected Serious Adverse Reaction (SUSAR):

Any untoward medical occurrence that at any dose:

- results in death,
The death of a patient is not per se an AE but an outcome. “Death” should be considered as a SAE only in case of “unexplained death” when no cause is identified. The event that resulted in a fatal outcome should be determined and reported as the SAE.
- is life threatening,

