9.3. Adverse event / Serious adverse event management

9.3.1. Data collection

Reporting in eCRF

At each visit, all Aes whether volunteered by the patient, discovered by study personnel during questioning, or detected through physical examination, laboratory test, or other means will be reported appropriately on the page “Adverse Events” of the eCRF (= AE page). The following items must be documented:

- nature of the event with self-explanatory and concise medical terminology (if possible indicate a diagnosis or syndrome instead of symptoms),

- date of onset and date of end (i.e. actual dates when the event starts and is resolved rather than dates when the Investigator is informed),
- intensity,
- evaluation of seriousness,
- relation to study treatment (separate evaluation for TG4001, avelumab), or to study procedures,
- action taken regarding the study treatment (separately for TG4001, avelumab),
- action taken regarding the event,
- outcome.

AE / AR requiring therapy must be treated with recognized standards of medical care to protect the health and well-being of the patient. Any treatment given will be reported on the page “Concomitant medication” of the eCRF.

Appropriate resuscitation equipment and medicines must be available to ensure the best possible treatment of an emergency situation.

Intensity

The intensity of AE/SAE will be graded according to the NCI CTCAE (version 4.03 dated 14 June 2010 for phase Ib and phase II part 1, version 5.0 dated 27 November 2017 for phase II part 2), which will be provided to the Investigators.

Should an event be missing in the CTCAE, the following 5-point scale is to be used:

Mild:	Discomfort noticed, but no disruption of normal daily activity
Moderate:	Discomfort sufficient to affect normal daily activity
Severe:	Inability to work or perform normal daily activity
Life-threatening:	Risk of death at the time of the event
Fatal:	The patient died

The correspondence between the two scales is as follows:

CTCAE	5-point scale
1	Mild
2	Moderate
3	Severe
4	Life-threatening
5	Fatal

Any increase in severity category during the course of an adverse event should be reported on the AE page of the eCRF with corresponding dates.

Relationship to the IMP(s)

The relationship to the IMPs (separate evaluation for TG4001 and avelumab) of each AE/SAE will be evaluated by the Investigator with the “global introspection” method using the following levels:

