10.4. Statistical and analytical plans

10.4.1. Safety analyses

All safety analyses will be performed and summarized in the SAF.

Adverse Events

AE summaries will include all AEs starting on or after start of study treatment or that has worsened on or after start of study treatment and starting no later than 90 days after the date of last study treatment administration.

All Aes, significant Aes, Aes leading to discontinuation of study treatment (overall and by component: TG4001, avelumab), severe Aes (Grade 3 or 4) and serious Aes (SAE) will be listed and summarized by System Organ Class (SOC) and Preferred Term (PT), intensity (based on the NCI CTCAE grades, also referred as CTCAE), relationship to study treatment (TG4001 and/or avelumab).

Separate AE summaries will be presented by SOC, PT, and CTCAE grade. In the summaries presented by grade, all Aes will be pooled. Specific tables will summarize related Aes to IMP and Aes of specific interest (injection site reactions).

The frequency of CTCAE Grade 3 and 4 Aes will be summarized separately.

Written narratives will be produced for all SAEs and unexpected or other significant Aes that are judged to be of special interest because of their clinical importance.

Adverse events/SAEs occurring after signing the Informed Consent Form (ICF) but before starting study treatment, including those observed in patients screened but not included will be listed separately from those occurring after treatment start.

Fatal Events

All fatal events will be listed and summarized by System Organ Class (SOC) and Preferred Term (PT). The nature of the event leading to death should be recorded. Sudden/unexplained death will be coded as “death”.

Fatal events will be summarized by presenting the number and percentage of patients who died. Data will be presented by SOC and PT using MedDRA coding.

Fatal events occurring after signing the Informed Consent Form (ICF) but before starting study treatment in patients screened but not included will be listed separately from those occurring after treatment start.

Laboratory abnormalities

The summaries will include all laboratory assessments collected no later than 30 days after treatment discontinuation. All laboratory assessments will be listed and those collected during 30 days after study treatment discontinuation will be flagged in the listings.

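### Non-serious adverse events between consent and start of study treatment are kept off the AE page, so non-serious harms of a baseline study biopsy cannot be identified as procedure-related

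*Combined protocol and SAP*

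**What the plan says.** Section 9.1 sets the scope: "An AE for the purposes of this protocol is a medical occurrence or deterioration of a pre-existing medical condition occurring after signing the informed consent". Its adverse-reaction definition reaches beyond the two products to study-specific procedures. Section 9.2 begins in the same spirit: "The study period during which all Aes and SAEs must be reported begins after informed consent is obtained".

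Further down, section 9.2 gives the page instructions. For events before treatment: "If an Adverse Event occurs during the screening period (i.e., after ICF signature and before start of study treatment), it will be recorded either on". Two destinations follow: the history/current-conditions page if there is an identified syndrome, and the signs-and-symptoms page if there is not. After that: "From start of study treatment, AEs will be recorded on an" AE page. One exception bridges the two periods: "In case of worsening of a medical condition which started before start of study treatment, an AE page will be completed".

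Section 9.3.1 says that AEs found at each visit go on the AE page and lists what that page must document, including intensity, seriousness, outcome and "relation to study treatment (separate evaluation for TG4001, avelumab), or to study procedures".

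Section 7.1 and footnote g of the flow-charts (Appendices IIIA and IIIC) follow the narrower rule: SAEs from consent, other AEs only from start of study treatment. Section 7.2 likewise asks for SAE reporting alone at baseline.

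Section 10.4.1 plans an output that assumes the wider rule: "Adverse events/SAEs occurring after signing the Informed Consent Form (ICF) but before starting study treatment, including those observed in patients screened but not included" are to be listed apart from later events.

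A tumour biopsy falls in this window. Section 7.2 makes it compulsory in phase Ib and phase II part 1, and "mandatory only for patients with accessible lesions in phase II part 2".

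**The concern.** The protocol makes three commitments: AEs count from consent, AEs go on the AE page, and pre-treatment AEs will be listed. Its page instructions do not deliver them for non-serious events. What is lost is the assessment rather than the bare fact of the event. Once a post-biopsy complication sits on a history or symptoms page, nothing in the documents says that it is graded or that anyone records whether the procedure caused it.

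At stake is the account of harm from a procedure that the protocol itself requires. On-treatment biopsies in phase II part 2 (Day 85, Month 9) come after the AE page has opened, so the same complication would be graded and attributed there. The baseline biopsy is treated differently only because of its timing.

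**Working it through.** No arithmetic applies and no figure in the plan needs reproducing. The check sets the sections side by side and follows each kind of event.

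**When the AE page opens.** The definitions table sets start of study treatment at Day 1 in phase Ib and phase II part 1, and at randomization in phase II part 2. The window in question therefore runs from consent to Day 1, or from consent to randomization. Under section 6.4.2 the avelumab-alone arm starts dosing about a week after randomization. Events in that week already go on the AE page and are not part of the gap.

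**Where an event starting in the window goes.**

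| Event | Where recorded | Grade and relation to procedure |
|---|---|---|
| Serious | Collected and sent to the sponsor from consent, whatever the cause (7.1, 7.2, 9.5, footnote g) | Graded under 9.3.1; unexpected procedure-related SAEs fall within the SUSAR definition in 9.1 |
| Non-serious, later worsens on treatment | History or symptoms page, then an AE page for the worsening (9.2) | Described for the worsening only |
| Non-serious, does not worsen | History or symptoms page only (9.2, 7.1) | Not described |

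The gap is the third row, and the initial episode in the second. Section 9.6 narrows it further, because a clinical AE of Grade 4 must be reported as an SAE. What remains among clinical events is non-serious events below Grade 4.

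**What the history and symptoms pages do hold.** Section 7.1 describes diagnosed conditions that begin in screening, with recovered or ongoing status, and relevant signs and symptoms present at consent or beginning in screening. Onset in screening is therefore foreseen, and a basic outcome is foreseen for diagnosed conditions. CTCAE grade and relation to study procedures are not mentioned for either page.

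**What the 10.4.1 listing could contain.** Pre-treatment SAEs are available. Non-serious events could be drawn from the history and symptoms pages by onset date, but such a listing could not separate a biopsy complication from an unrelated intercurrent illness by any recorded relationship. For screen failures, section 6.4.1 requires the reason for non-inclusion and only minimal further data, so the non-serious part of the promised listing may have no source.

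**Which biopsies are exposed.** Only a biopsy done after consent and for the study can generate an event here. Inclusion criterion 1 (section 4.1) allows a phase II part 2 biopsy to count as normal care, in which case it may precede consent. Inclusion criterion 10 accepts archival tissue when the tumour is not accessible. The number of exposed patients therefore cannot be derived. The figure of at least 80 randomised patients in section 3.1.2 is a recruitment target, not a count of such biopsies.

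**The case against.** The best defence is that this is a consistent design choice. Section 7.1, section 7.2 and footnote g all apply the same split. The opening sentence of 9.2 can be read as a reporting window and the later sentences as instructions on which page to use. Section 10.4.1 does not say that its listing draws only on AE pages. No endpoint, dosing decision or comparison between arms depends on these events. With phase Ib complete and the part 2 interim analysis already described in section 3.2 as having set the final event target, a change now would reach only the remaining patients and would leave two collection rules in one database.

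Part of this stands. The split is applied consistently at the collection end, a partial listing is possible, and the late timing is a real cost. It does not answer the missing grade and procedure attribution, nor does it reconcile collection with 9.1, 9.3.1 and 10.4.1.

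Three stronger readings are tempting, and the documents do not support them:

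- A reader might infer that harms of the screening biopsy never reach the safety data. They do if they are serious, and in part if they worsen after treatment start.
- A reader might infer that only SAEs could populate the pre-treatment listing, or that recorded non-serious events would be zero. Section 7.1 foresees conditions with onset in screening, so they can be retrieved, though not attributed.
- A reader might blame this rule for making a screening complication the baseline against which later worsening is judged. That follows from the TEAE definition in 9.1 (absent before treatment, or worsened since) and would remain after any change to the recording page.

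**Conclusion.** The point holds in a limited form. For non-serious events between consent and start of study treatment, the collection rule conflicts with the all-AEs-from-consent sentence in 9.2, the AE-page rule in 9.3.1, the reach of the adverse-reaction definition in 9.1, and the pre-treatment listing in 10.4.1. Non-serious harm from a baseline biopsy done after consent for the study cannot be identified as procedure-related.

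The size is small and not quantifiable: the documents give neither the number of exposed biopsies nor a complication rate. SAE capture is intact. Treatment-emergent summaries are unaffected, because 10.4.1 counts only events that start or worsen on or after start of study treatment. The conclusion assumes that the history and symptoms pages hold no more than the protocol describes. If the eCRF already carries grade and procedure relation on those pages, the gap reduces to wording. This is a worthwhile improvement rather than a threat to the trial's conclusions.

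**What to change.** In section 9.2, state that any AE related to a study-specific procedure is recorded on the AE page from consent, with grade, outcome and relation to the procedure, and that this applies to screen failures too. Other non-serious conditions arising in screening can stay on the history and symptoms pages. Limit the pre-treatment listing in 10.4.1 to SAEs and these procedure-related AEs, so that what is listed matches what is collected. Align sections 7.1 and 7.2 and footnote g of the flow-charts, and add a line to the eCRF completion guideline.

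The cost is a sentence in 9.2 with its consequential edits, the guideline line, and a few more AE pages at screening. Patients already enrolled will have been collected under the present rule. The clinical study report should say so and should not pool the two periods as if procedure-related events had been sought in the same way throughout.

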9.3. Adverse event / Serious adverse event management

9.3.1. Data collection

Reporting in eCRF

At each visit, all Aes whether volunteered by the patient, discovered by study personnel during questioning, or detected through physical examination, laboratory test, or other means will be reported appropriately on the page “Adverse Events” of the eCRF (= AE page). The following items must be documented:

- nature of the event with self-explanatory and concise medical terminology (if possible indicate a diagnosis or syndrome instead of symptoms),

- date of onset and date of end (i.e. actual dates when the event starts and is resolved rather than dates when the Investigator is informed),
- intensity,
- evaluation of seriousness,
- relation to study treatment (separate evaluation for TG4001, avelumab), or to study procedures,
- action taken regarding the study treatment (separately for TG4001, avelumab),
- action taken regarding the event,
- outcome.

AE / AR requiring therapy must be treated with recognized standards of medical care to protect the health and well-being of the patient. Any treatment given will be reported on the page “Concomitant medication” of the eCRF.

Appropriate resuscitation equipment and medicines must be available to ensure the best possible treatment of an emergency situation.

Intensity

The intensity of AE/SAE will be graded according to the NCI CTCAE (version 4.03 dated 14 June 2010 for phase Ib and phase II part 1, version 5.0 dated 27 November 2017 for phase II part 2), which will be provided to the Investigators.

Should an event be missing in the CTCAE, the following 5-point scale is to be used:

Mild:	Discomfort noticed, but no disruption of normal daily activity
Moderate:	Discomfort sufficient to affect normal daily activity
Severe:	Inability to work or perform normal daily activity
Life-threatening:	Risk of death at the time of the event
Fatal:	The patient died

The correspondence between the two scales is as follows:

CTCAE	5-point scale
1	Mild
2	Moderate
3	Severe
4	Life-threatening
5	Fatal

Any increase in severity category during the course of an adverse event should be reported on the AE page of the eCRF with corresponding dates.

Relationship to the IMP(s)

The relationship to the IMPs (separate evaluation for TG4001 and avelumab) of each AE/SAE will be evaluated by the Investigator with the “global introspection” method using the following levels:

- **Not related:** the temporal relationship of the clinical event to the administration of avelumab and TG4001 (separate evaluation) makes a causal relationship unlikely; and other drugs, therapeutic interventions or underlying conditions provide a sufficient explanation for the observed event.
- **Related:** the temporal relationship of the clinical event to the administration of avelumab and TG4001 (separate evaluation) makes a causal relationship possible; and other drugs, therapeutic

interventions or underlying conditions do not provide a sufficient explanation for the observed event. A clear-cut temporal association with improvement on cessation of the study drug or recurrence upon rechallenge may also be observed.

Outcome

The outcome is rated as follows:

- recovered,
- not recovered,
- recovered with sequelae,
- fatal,
- unknown.

Note on “fatal”: this outcome is to be used only for the event leading to death. The outcome of all other events at the time of the death must be reported. The outcome of ongoing ones is reported as “not recovered”.

Action taken regarding TG4001/avelumab

Action taken will be provided separately for each study treatment.

- None: TG4001/avelumab administration continues as planned in the protocol, or has not yet been administered and no action is planned
- Cancelled: TG4001/avelumab administration following the occurrence of the event is cancelled
- Stopped: TG4001/avelumab is definitively stopped
- Not applicable: TG4001/avelumab administration is already stopped

Action taken regarding the event:

- New treatment prescribed or change in concomitant medication
- Hospitalization or prolongation of hospitalization
- Non-drug therapy implemented
- None
- Other (to be specified)

An AE/SAE requiring therapy must be treated with recognized standards of medical care to protect the health and well-being of the patient. Any medication or non-drug therapy given will be reported on the eCRF pages dedicated to the collection of concomitant medications.

